4.5.4.1 Secondary Endpoints

The secondary endpoints for this study and associated time points for analysis are listed in Table 5.

Table 5. Secondary Safety Endpoints and Scheduled Measurements of Secondary Endpoints*

Safety Endpoints	Pre-Infusion	Post-Infusion			
		0.5 Hours	4 Hours	24 Hours	28 Days
Vital Signs:					
Blood Pressure	X	X	X		
Heart Rate	X	X	X		
Respiration Rate	X	X	X		
Temperature	X	X	X		
Urinalysis:					
Glucose	X	X	X		
Ketones	X	X	X		
Protein	X	X	X		
Blood	X	X	X		
Leukocyte Esterase	X	X	X		
Nitrite	X	X	X		
Bilirubin	X	X	X		
Hematology:					
Hematocrit	X	X	X	X	
Hemoglobin	X	X	X	X	
Platelet Count	X	X	X	X	
RBC Count	X	X	X	X	
WBC Count	X	X	X	X	
Direct Antiglobulin Test (DAT) (IgG and C3)	X				
Clinical Chemistry:					
ALP	X	X	X		
ALT	X	X	X		
AST	X	X	X		
Ionized Calcium	X	X			
Total Magnesium	X	X			
pH	X	X			
Electrolytes (Calcium, Chloride, Potassium, Sodium, Lactic Acid, and Bicarbonate)	X	X	X		
Glucose	X	X	X		
Total Bilirubin	X	X	X		
Total Protein	X	X	X		
BUN	X	X	X		
Creatinine	X	X	X		
Coagulation Tests:					
PT	X	X	X	X	X
INR	X	X	X	X	X
aPTT	X	X	X	X	X
D-dimer	X	X	X	X	
Cohort 3 safety analyses will also include measurements taken at each Infusion Visit at the following post-infusion time points.					
Factor I	X	X	X		
Factor II	X	X	X		
Factor V	X	X	X		

Safety Endpoints	Pre-Infusion	Post-Infusion			
		0.5 Hours	4 Hours	24 Hours	28 Days
Factor VII	X	X	X		
Factor VIII	X	X	X		
Factor IX	X	X	X		
Factor X	X	X	X		
Factor XI	X	X	X		
von Willebrand Factor Activity	X	X	X		
Protein C Activity	X	X	X		
Protein S Activity	X	X	X		
PF 1+2	X	X			
TAT	X	X			
Antithrombin III	X	X			
Alpha-2 Antiplasmin	X	X			
C3a des Arg	X	X			

* Grayed cells mean that the time point either was not measured or will not be used in the analysis.

4.5.4 Conduct Exploratory Analyses Comparing FDP-ACD to FFP (Secondary Objective #2)

The analyses conducted for secondary objective #1 will be used to meet secondary objective #2. In addition, descriptive statistics on a post-infusion, abnormal coagulation function assay, which is greater than a 20% change in either direction from baseline for PT/INR and/or aPTT values, will be presented using separate shift tables. Shift tables based on the upper limit of normal (ULN) will also be provided for D-dimer, prothrombin fragment (PF) 1+2, thrombin-antithrombin complex (TAT) and C3a des Arg.

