## 11.1.2.2. Exploratory Analyses Comparing FDP to FFP (Secondary Objective 2)

The analyses conducted for secondary objective 1 will be used to meet secondary objective 2. In addition, descriptive statistics on a post-infusion, abnormal coagulation function assay that is greater than a 20% change in either direction from baseline for PT/INR and/or aPTT values will be presented using separate shift tables. Shift tables based on the upper limit of normal (ULN) will also be provided for D-dimer, PF 1+2, TAT, and C3a des Arg.

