Programming Note: This table will also be repeated for Cohort 3 (Table 10.19-10.27) for the first infusion:

- Urinalysis:
 - Glucose (Table 10.19)
 - Ketones (Table 10.20)
 - Protein (Table 10.21)
 - Blood (Table 10.22)
 - Leukocyte esterase (Table 10.23)
 - Nitrite (Table 10.24)
 - Bilirubin (Table 10.25)
- Direct Antiglobulin Test (DAT):
 - Immunoglobulin G (Table 10.26)
 - Complement C3 (Table 10.27)

Note: a=Denominator for each % is the treatment group N.

Programming Note: This table will also be repeated for Cohort 3 (Table 10.28-10.36) for the second infusion:

- Urinalysis:
 - Glucose (Table 10.28)
 - Ketones (Table 10.29)
 - Protein (Table 10.30)
 - Blood (Table 10.31)
 - Leukocyte esterase (Table 10.32)
 - Nitrite (Table 10.33)
 - Bilirubin (Table 10.34)
- Direct Antiglobulin Test (DAT):
 - Immunoglobulin G (Table 10.35)
 - Complement C3 (Table 10.36)

Programming Note: For Cohort 3, the treatment arms will be unmasked for final data analysis once the study has been unblinded. The titles for Cohort 3 are shown below:

Table XX. Measures (Percentage) Over Time Since Treatment Emergent Change
XX Measures (Percentage) Over Time Since Treatment Emergent Change – Cohort 3 (810 mL) – Infusion #1
Safety Population – S3 (N=XX)
FDP-1
Phase I

Table XX. Measures (Percentage) Over Time Since Treatment Emergent Change
XX Measures (Percentage) Over Time Since Treatment Emergent Change – Cohort 3 (810 mL) – Infusion #2
Safety Population – S3 (N=XX)
FDP-1
Phase I

Note: a=Denominator for each % is the treatment group N.

Table 11.1. – Table 11.34. Shift Table Summary of Number of Subjects with Absolute Laboratory Values for XX Measure (Unit) Pre-Infusion vs. Max Post-Infusion

**Absolute Lab Values for XX Measure (Unit) Pre-Infusion vs. Max Post- Infusion – Cohort 1 (270 mL)
 Safety Population – S3 (N=XX)**

**FDP-1
 Phase I**

Treatment	Treatment Emergent High		
	N	n	%
FDP-CPD			
FDP-ACD			

Programming Note: This table will be produced for the following endpoints for Cohort 1 (Table 11.1-11.4):

- Coagulation Factor Tests:
 - PT (Table 11.1)
 - INR (Table 11.2)
 - aPTT (Table 11.3)
 - D-Dimer (ug/mL FEU) (Table 11.4)

Programming Note: This table will be produced for the following endpoints for Cohort 2 (Table 11.5-11.8):

- Coagulation Factor Tests:
 - PT (Table 11.5)
 - INR (Table 11.6)
 - aPTT (Table 11.7)
 - D-Dimer (ug/mL FEU) (Table 11.8)

The titles for Cohort 2 is listed below:

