Table XX. Shift Table Summary of Number of Subjects with Absolute Laboratory Values for XX Measure (Unit) Pre-Infusion vs. Max Post-Infusion

Absolute Laboratory Values for XX Measure (Unit) Pre-Infusion vs. Max Post- Infusion – Cohort 2 (540 mL)

N=number of subjects with pre-infusion ‘normal’ and at least one post-infusion value; n=among the ‘N’, number of subjects with Max. post-infusion ‘high’. High will be a greater than or equal to 20% increase from pre-infusion for PT, INR and aPTT and greater than the upper limit of normal (ULN) for all other endpoints except for D-Dimer. Normal will be a less than 20% increase from pre-infusion for PT, INR, and aPTT and lower than or equal to the ULN for all other endpoints except for D-Dimer. D-Dimer will be converted to a categorical variable where normal will be < 0.5 ug/mL FEU and high will be \geq 0.5 ug/mL FEU.

80

Program Path:

Data source:AD LB Cross Reference: Listing 26-27

Data extract date:

Safety Population – S3 (N=XX)

FDP-1

Phase I

Programming Note: For Cohort 3, the treatment arms will be unmasked for final data analysis once the study has been unblinded. This table will be produced for the following endpoints for Cohort 3 for the first infusion (Table 11.9-11.15):

- Coagulation Factor Tests:
 - PT (Table 11.9)
 - INR (Table 11.10)
 - aPTT (Table 11.11)
 - D-Dimer (ug/mL FEU) (Table 11.12)
 - PF 1+2 (pmol/L) (Table 11.13)
 - TAT (ng/mL) (Table 11.14)
 - C3a des Arg (ng/mL) (Table 11.15)

Programming Note: This table will be produced for the following endpoints for Cohort 3 for the second infusion (Table 11.16-11.22):

- Coagulation Factor Tests:
 - PT (Table 11.16)
 - INR (Table 11.17)
 - aPTT (Table 11.18)
 - D-Dimer (ug/mL FEU) (Table 11.19)
 - PF 1+2 (pmol/L) (Table 11.20)
 - TAT (ng/mL) (Table 11.21)
 - C3a des Arg (ng/mL) (Table 11.22)

Programming Note: For Cohort 3, the treatment arms will be unmasked for final data analysis after the study has been unblinded.

Table XX. Shift Table Summary of Number of Subjects with Absolute Laboratory Values for XX Measure (Unit) Pre-Infusion vs. Max Post-Infusion

Absolute Laboratory Values for XX Measure (Unit) Pre-Infusion vs. Max Post- Infusion – Cohort 3 (810 mL) – Infusion #1 Safety Population – S3 (N=XX)

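### Table 11 is the only summary table for D-dimer, PF 1+2, TAT and C3a des Arg, and it leaves out every subject already high before infusion, so a further rise in such a subject reaches no laboratory summary table

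*SAP*

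**What the plan says.** Protocol 11.1.2.2 commits to the display for secondary objective 2: "Shift tables based on the upper limit of normal (ULN) will also be provided for D-dimer, PF 1+2, TAT, and C3a des Arg". The second of the two SAP sections numbered 4.5.4 (Secondary Objective #2) repeats it: "Shift tables based on the upper limit of normal (ULN) will also be provided for D-dimer, prothrombin fragment (PF) 1+2, thrombin-antithrombin complex (TAT", with C3a des Arg completing the list. The other SAP section 4.5.4 (Secondary Objective #1) goes further: it promises descriptive statistics on change from baseline for the Cohort 3 measures in SAP Table 5, wherever that is appropriate. Table 5 lists all four markers.

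The shells in SAP section 5 carry the four markers in Table 11 only. Its title sets pre-infusion against maximum post-infusion values, but the body has a single block, "Treatment Emergent High", with N, n and a percentage for each product. The footnote defines N as the "number of subjects with pre-infusion ‘normal’ and at least one post-infusion value". It defines n, among that N, as the "number of subjects with Max. post-infusion ‘high". For PF 1+2, TAT and C3a des Arg, high means "greater than the upper limit of normal (ULN) for all other endpoints except for D-Dimer". For D-dimer the rule is a fixed cut: "D-Dimer will be converted to a categorical variable where normal will be < 0.5 ug/mL FEU", and high otherwise.

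SAP 4.4.2 takes baseline from the draw made at the Infusion Visit just before infusion, not from screening.

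**The concern.** A reader who expects a table of category before against category after will find only one of its four cells, normal to high. The row for subjects who start high is missing. If no other summary table picks those subjects up, the size and direction of their change go unsummarised.

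All four markers are named secondary endpoints (protocol 6.4.2), and D-dimer is also part of the DVT determination in the stopping rules (protocol 6.5). The crossover in Cohort 3 exists so that FDP and FFP can be compared within the same subject. A denominator that depends on each infusion's own baseline can keep a subject for one product and drop the same subject for the other.

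**Working it through.** No sample size or test enters this point, so the check is a count of the laboratory shells followed by a worked example.

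**1. Are all laboratory tables accounted for?** The programming notes reproduce the numbering in the table titles:
- Table 9 (change from baseline): 30 in Cohort 1, 30 in Cohort 2, and 43 for each Cohort 3 infusion. 30 + 30 + 43 + 43 = 146, as stated.
- Table 10 (urinalysis and DAT percentages): 4 × 9 = 36, as stated.
- Table 11: high versions 4 + 4 + 7 + 7 = 22; low versions, for PT, INR and aPTT only, 3 × 4 = 12. 22 + 12 = 34, as stated.
- Table 12 (sequence by period): 5 + 17 + 3 + 13 = 38, as stated.
- Table 13: DAT only, 2 tables.
- Figure 4 (individual plots, Cohort 3): 3 + 8 + 3 + 5 = 19, as stated.

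**2. Where do the four markers appear?**
- Table 9: the coagulation list stops at aPTT for Cohorts 1 and 2 and at alpha-2 antiplasmin for Cohort 3. None of the four is there.
- Table 12: the list also stops at alpha-2 antiplasmin. None is there.
- Table 11: D-dimer in 11.4, 11.8, 11.12 and 11.19; PF 1+2, TAT and C3a des Arg in 11.13 to 11.15 and 11.20 to 11.22. That is 4 + 3 × 2 = 10 tables.
- Figures 4.15, 4.16 and 4.19 show PF 1+2, TAT and C3a des Arg. D-dimer has no figure.
- Listings 28 and 29 give coagulation results subject by subject with the normal range and a high/low flag. Table 11's own cross-reference points to Listings 26 and 27, which are urinalysis.

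The number of laboratory summary tables that would show a further rise in a subject high before infusion is therefore 0 for each marker.

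**3. Can a subject be high at baseline?** Eligibility excludes D-dimer of 0.5 or more at screening, but screening is scheduled about seven to twelve weeks before Day 1 (Study Days -56 to -49, or -84 to -77 for Arm 3). The baseline for Cohort 3 infusion #2 is drawn around Day 15, after the first product. The other three markers have no eligibility limit and are first measured just before infusion.

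**4. What one such subject does.** Take a Cohort 3 product group of 4. One subject is high before infusion and rises further; one of the other three moves from normal to high.
- Table 11 as planned: n/N = 1/3 = 33.3%. The fourth subject is absent.
- All evaluable subjects cross-classified: normal to high 1/4 = 25%, high to high 1/4 = 25%, normal to normal 2/4 = 50%.

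**5. How often?** The documents give no pre-infusion-high rate. If a rate p is assumed, with subjects independent, a group of 4 loses at least one with probability 1 - (1 - p)^4: 18.5% at p = 5%, 34.4% at 10%, 68.4% at 25%. These show only how the arithmetic behaves; no value of p is supported by the documents.

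**The case against.** The other side has real substance.

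- **The values are not hidden.** PF 1+2, TAT and C3a des Arg have one pre-infusion and one 0.5-hour value each, and with 8 subjects a rise can be read off the individual plots. The listings hold every result, and the protocol synopsis allows data to be shown as listings, tables or figures. A rise recorded as an adverse event would also enter the AE tables. A reader might infer that such a rise is not reported at all; the documents do not support that. This stands, except that D-dimer has listings only.
- **The denominator is declared.** N is printed beside n, and the footnote defines it. A reader might infer that the product groups would differ for no stated reason; that is not so.
- **A normal-to-high count is a recognised format.** The SAP takes its shells from the phUSE white papers, one of which concerns shifts from normal to abnormal, and neither document defines a shift table as four cells. So the display is not illegitimate. It still summarises less than its title and the text suggest.
- **The stakes are limited.** The analysis is headed exploratory. Protocol 8.2.2 describes PF 1+2, TAT and C3a des Arg as research tests not used to assess subject safety, and protocol 6.1 rests the safety conclusion on TEAEs alone. D-dimer is screened, rechecked before infusion and reviewed before release. A reader might infer a gap in subject monitoring; there is none here. The point concerns how results are summarised.

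What remains is the promised change-from-baseline summary. Its qualifier leaves room for judgement, but the SAP gives no reason why change is inappropriate for these four when it is tabulated for the other coagulation tests.

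**Conclusion.** The point holds as a reporting defect. For 10 of the 34 Table 11 shells, a stated denominator rule removes subjects who are high before infusion from the only summary table their marker has. Each one takes 1 of 4 from a product group. In Cohort 3 a subject normal before infusion #1 and high before infusion #2 is counted for one product and not the other, which weakens the within-subject comparison. D-dimer is most exposed, with neither a figure nor a change table.

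The conclusion rests on the shells as numbered and on 4 subjects per product group at each infusion. It makes no claim about how many subjects will be affected, and if none is high before infusion Table 11 loses nobody. The primary safety analysis is untouched. The change is worth making before the tables are programmed.

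**What to change.** 1. In the 10 Table 11 shells for these markers, include every subject with a pre-infusion and at least one post-infusion value. Cross-classify pre-infusion normal/high by maximum post-infusion normal/high, and keep treatment-emergent high as one of the four cells. For the high-to-high cell, state how many subjects rose above their own pre-infusion value.
2. Add the four markers to Tables 9 and 12 so that the size of change is summarised, with D-dimer included where numeric values are reported. This adds 4 + 3 × 2 = 10 tables to Table 9 and 4 to Table 12. SAP Table 5 lists D-dimer at 24 hours, whereas the Table 9 and 12 notes stop at 4 hours outside hematology, so the time points shown should be stated.
3. Correct the Table 11 cross-reference to Listings 28 and 29. Say whether D-dimer is classified by the ULN, as the text has it, or by the fixed 0.5 cut in the footnote.

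The cost is three extra cells per product in ten existing tables, 14 further tables from existing shells, and footnote edits. No new samples, tests or visits are needed.

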5. PROPOSED SUMMARY TABLES, LISTINGS, AND GRAPHS

The tables, listings, and figures were created using the templates from the Pharmaceutical Users Software Exchange (phUSE) [whitepapers](#). The references are at the end of the SAP. The letter “X” is used as a placeholder in the table numbers, sample sizes, measurement names, and in the presentation of data and represents the next sequential table number, appropriate sample size, the next sequential measurement name or data presentation format as appropriate according to the programming instructions.

Table 1.1.- Table 1.15. Demographic and Clinical Characteristics Summary
Baseline Demographics and Clinical Characteristics – Cohort 1 (270 mL)
Full Analysis Population – F1 (N=XX)
FDP-1
Phase I

Demographic Parameter and Clinical Characteristics		FDP-CPD (N=XX)	FDP-ACD (N=XX)	Total (N=XX)
Sex n (%)	n ^a	xx	xx	xx
	F	xx(x.x)	xx(x.x)	xx(x.x)
	M	xx(x.x)	xx(x.x)	xx(x.x)
	Missing	xx	xx	xx
Age (years)	n ^a	xx	xx	xx
	Mean	xx.x	xx.x	xx.x
	SD	xx.x	xx.x	xx.x
	Median	xx.x	xx.x	xx.x
	Q1, Q3	xx,xx	xx,xx	xx,xx
	Min, Max	xx,xx	xx,xx	xx,xx
	Missing	xx	xx	xx
Race n (%)	n ^a	xx	xx	xx
	American Indian or Alaska Native	xx(x.x)	xx(x.x)	xx(x.x)
	Asian	xx(x.x)	xx(x.x)	xx(x.x)
	Black or African American	xx(x.x)	xx(x.x)	xx(x.x)
	Native Hawaiian or Other Pacific Islander	xx(x.x)	xx(x.x)	xx(x.x)
	White	xx(x.x)	xx(x.x)	xx(x.x)
	Multiple	xx(x.x)	xx(x.x)	xx(x.x)
	Missing	xx	xx	xx
Ethnicity n (%)	n ^a	xx	xx	xx
	Hispanic	xx(x.x)	xx(x.x)	xx(x.x)
	Non-Hispanic or Latino	xx(x.x)	xx(x.x)	xx(x.x)
	Missing	xx	xx	xx
Is the subject of childbearing potential? n (%)	n ^a	xx	xx	xx
	Yes	xx(x.x)	xx(x.x)	xx(x.x)
	No	xx(x.x)	xx(x.x)	xx(x.x)
	Missing	xx	xx	xx
Blood Type n (%)	n ^a	xx	xx	xx
	A	xx(x.x)	xx(x.x)	xx(x.x)
	B	xx(x.x)	xx(x.x)	xx(x.x)
	AB	xx(x.x)	xx(x.x)	xx(x.x)
	O	xx(x.x)	xx(x.x)	xx(x.x)
Rh Factor n (%)	n ^a	xx	xx	xx
	Negative	xx(x.x)	xx(x.x)	xx(x.x)
	Positive	xx(x.x)	xx(x.x)	xx(x.x)
Height (cm)	n ^a	xx	xx	xx
	Mean	xx.x	xx.x	xx.x
	SD	xx.x	xx.x	xx.x
	Median	xx.x	xx.x	xx.x
	Q1, Q3	xx,xx	xx,xx	xx,xx
	Min, Max	xx,xx	xx,xx	xx,xx

Note: Abbreviations: N=Number of subjects in the population; Q1=25% Percentile; Q3=75% Percentile; and SD=Standard Deviation.

^a=Number of subjects with non-missing data, used as the denominator.

The variable 'Has the subject ever experienced any diseases and/or surgeries?' will only use the data at screening.

Demographic Parameter and Clinical Characteristics		FDP-CPD (N=XX)	FDP-ACD (N=XX)	Total (N=XX)
	Missing	xx	xx	xx
Weight (kg)	n ^a	xx	xx	xx
	Mean	xx.x	xx.x	xx.x
	SD	xx.x	xx.x	xx.x
	Median	xx.x	xx.x	xx.x
	Q1, Q3	xx,xx	xx,xx	xx,xx
	Min, Max	xx,xx	xx,xx	xx,xx
	Missing	xx	xx	xx
BMI n (%)	n ^a	xx	xx	xx
	Underweight (<18.5)	xx(x.x)	xx(x.x)	xx(x.x)
	Normal (18.5-<25)	xx(x.x)	xx(x.x)	xx(x.x)
	Overweight (25.0-<30)	xx(x.x)	xx(x.x)	xx(x.x)
	Obese (≥30)	xx(x.x)	xx(x.x)	xx(x.x)
	Missing	xx	xx	xx
BMI (kg/m²)	n ^a	xx	xx	xx
	Mean	xx.x	xx.x	xx.x
	SD	xx.x	xx.x	xx.x
	Median	xx.x	xx.x	xx.x
	Q1, Q3	xx,xx	xx,xx	xx,xx
	Min, Max	xx,xx	xx,xx	xx,xx
	Missing	xx	xx	xx
Has the subject ever experienced any diseases and/or surgeries?	n ^a	xx	xx	xx
	Yes	xx(x.x)	xx(x.x)	xx(x.x)
	No	xx(x.x)	xx(x.x)	xx(x.x)

Note: Abbreviations: N=Number of subjects in the population; Q1=25% Percentile; Q3=75% Percentile; and SD=Standard Deviation.

^a=Number of subjects with non-missing data, used as the denominator.

The variable 'Has the subject ever experienced any diseases and/or surgeries?' will only use the data at screening.

Table 1.1.- Table 1.15 (Open). Demographic and Clinical Characteristics Summary
Baseline Demographics and Clinical Characteristics – Cohort 3 (810 mL)
Full Analysis Population – F1 (N=XX)
FDP-1
Phase I

Demographic Parameter and Clinical Characteristics		Total (N=XX)
Sex n (%)	n ^a	XX
	F	xx(x.x)
	M	xx(x.x)
	Missing	XX
Age (years)	n ^a	XX
	Mean	XX.X
	SD	XX.X
	Median	XX.X
	Q1, Q3	XX,XX
	Min, Max	XX,XX
	Missing	XX
Race n (%)	n ^a	XX
	American Indian or Alaska Native	xx(x.x)
	Asian	xx(x.x)
	Black or African American	xx(x.x)
	Native Hawaiian or Other Pacific Islander	xx(x.x)
	White	xx(x.x)
	Multiple	xx(x.x)
	Missing	XX
Ethnicity n (%)	n ^a	XX
	Hispanic	xx(x.x)
	Non-Hispanic or Latino	xx(x.x)
	Missing	XX
Is the subject of childbearing potential? n (%)	n ^a	XX
	Yes	xx(x.x)
	No	xx(x.x)
	Missing	XX
Blood Type n (%)	n ^a	XX
	A	xx(x.x)
	B	xx(x.x)
	AB	xx(x.x)
	O	xx(x.x)
Rh Factor n (%)	n ^a	XX
	Negative	xx(x.x)
	Positive	xx(x.x)
Height (cm)	n ^a	XX
	Mean	XX.X
	SD	XX.X
	Median	XX.X
	Q1, Q3	XX,XX
	Min, Max	XX,XX
	Missing	XX

Note: Abbreviations: N=Number of subjects in the population; Q1=25% Percentile; Q3=75% Percentile; and SD=Standard Deviation.

^a=Number of subjects with non-missing data, used as the denominator.

The variable 'Has the subject ever experienced any diseases and/or surgeries?' will only use the data at screening.

Demographic Parameter and Clinical Characteristics		Total (N=XX)
Weight (kg)	n ^a	XX
	Mean	XX.X
	SD	XX.X
	Median	XX.X
	Q1, Q3	XX,XX
	Min, Max	XX,XX
	Missing	XX
BMI n (%)	n ^a	XX
	Underweight (<18.5)	xx(x.x)
	Normal (18.5-<25)	xx(x.x)
	Overweight (25.0-<30)	xx(x.x)
	Obese (≥ 30)	xx(x.x)
	Missing	XX
BMI (kg/m²)	n ^a	XX
	Mean	XX.X
	SD	XX.X
	Median	XX.X
	Q1, Q3	XX,XX
	Min, Max	XX,XX
	Missing	XX
Has the subject ever experienced any diseases and/or surgeries?	n ^a	XX
	Yes	xx(x.x)
	No	xx(x.x)

Note: Abbreviations: N=Number of subjects in the population; Q1=25% Percentile; Q3=75% Percentile; and SD=Standard Deviation.

^a=Number of subjects with non-missing data, used as the denominator.

The variable 'Has the subject ever experienced any diseases and/or surgeries?' will only use the data at screening.

Table 1.1.- Table 1.15 (Closed). Demographic and Clinical Characteristics Summary
Baseline Demographics and Clinical Characteristics – Cohort 3 (810 mL)
Full Analysis Population – F1 (N=XX)
FDP-1
Phase I

Demographic Parameter and Clinical Characteristics		A (N=XX)	B (N=XX)	Total (N=XX)
Sex n (%)	n ^a	xx	xx	xx
	F	xx(x.x)	xx(x.x)	xx(x.x)
	M	xx(x.x)	xx(x.x)	xx(x.x)
	Missing	xx	xx	xx
Age (years)	n ^a	xx	xx	xx
	Mean	xx.x	xx.x	xx.x
	SD	xx.x	xx.x	xx.x
	Median	xx.x	xx.x	xx.x
	Q1, Q3	xx,xx	xx,xx	xx,xx
	Min, Max	xx,xx	xx,xx	xx,xx
	Missing	xx	xx	xx
Race n (%)	n ^a	xx	xx	xx
	American Indian or Alaska Native	xx(x.x)	xx(x.x)	xx(x.x)
	Asian	xx(x.x)	xx(x.x)	xx(x.x)
	Black or African American	xx(x.x)	xx(x.x)	xx(x.x)
	Native Hawaiian or Other Pacific Islander	xx(x.x)	xx(x.x)	xx(x.x)
	White	xx(x.x)	xx(x.x)	xx(x.x)
	Multiple	xx(x.x)	xx(x.x)	xx(x.x)
	Missing	xx	xx	xx
Ethnicity n (%)	n ^a	xx	xx	xx
	Hispanic	xx(x.x)	xx(x.x)	xx(x.x)
	Non-Hispanic or Latino	xx(x.x)	xx(x.x)	xx(x.x)
	Missing	xx	xx	xx
Is the subject of childbearing potential? n (%)	n ^a	xx	xx	xx
	Yes	xx(x.x)	xx(x.x)	xx(x.x)
	No	xx(x.x)	xx(x.x)	xx(x.x)
	Missing	xx	xx	xx
Blood Type n (%)	n ^a	xx	xx	xx
	A	xx(x.x)	xx(x.x)	xx(x.x)
	B	xx(x.x)	xx(x.x)	xx(x.x)
	AB	xx(x.x)	xx(x.x)	xx(x.x)
	O	xx(x.x)	xx(x.x)	xx(x.x)
Rh Factor n (%)	n ^a	xx	xx	xx
	Negative	xx(x.x)	xx(x.x)	xx(x.x)
	Positive	xx(x.x)	xx(x.x)	xx(x.x)
Height (cm)	n ^a	xx	xx	xx
	Mean	xx.x	xx.x	xx.x
	SD	xx.x	xx.x	xx.x
	Median	xx.x	xx.x	xx.x
	Q1, Q3	xx,xx	xx,xx	xx,xx

Note: Abbreviations: N=Number of subjects in the population; Q1=25% Percentile; Q3=75% Percentile; and SD=Standard Deviation.

^a=Number of subjects with non-missing data, used as the denominator.

The variable 'Has the subject ever experienced any diseases and/or surgeries?' will only use the data at screening.

Demographic Parameter and Clinical Characteristics		A (N=XX)	B (N=XX)	Total (N=XX)
	Min, Max	xx,xx	xx,xx	xx,xx
	Missing	xx	xx	xx
Weight (kg)	n ^a	xx	xx	xx
	Mean	xx.x	xx.x	xx.x
	SD	xx.x	xx.x	xx.x
	Median	xx.x	xx.x	xx.x
	Q1, Q3	xx,xx	xx,xx	xx,xx
	Min, Max	xx,xx	xx,xx	xx,xx
	Missing	xx	xx	xx
BMI n (%)	n ^a	xx	xx	xx
	Underweight (<18.5)	xx(x.x)	xx(x.x)	xx(x.x)
	Normal (18.5-<25)	xx(x.x)	xx(x.x)	xx(x.x)
	Overweight (25.0-<30)	xx(x.x)	xx(x.x)	xx(x.x)
	Obese (≥30)	xx(x.x)	xx(x.x)	xx(x.x)
	Missing	xx	xx	xx
BMI (kg/m²)	n ^a	xx	xx	xx
	Mean	xx.x	xx.x	xx.x
	SD	xx.x	xx.x	xx.x
	Median	xx.x	xx.x	xx.x
	Q1, Q3	xx,xx	xx,xx	xx,xx
	Min, Max	xx,xx	xx,xx	xx,xx
	Missing	xx	xx	xx
Has the subject ever experienced any diseases and/or surgeries?	n ^a	xx	xx	xx
	Yes	xx(x.x)	xx(x.x)	xx(x.x)
	No	xx(x.x)	xx(x.x)	xx(x.x)

Programming Instruction: The variable 'Has the subject ever experienced any diseases and/or surgeries?' will only use the data at screening. This table will be repeated for all analysis populations that are determined to be on a different set of subjects as described in Section 4.2 for each cohort (Table 1.2 – Table 1.15). All tables may not be produced based on the table reduction method mentioned in Section 4.2 and may not exactly match the SAP. The table titles will indicate the cohort and population used for each table.

Note: Abbreviations: N=Number of subjects in the population; Q1=25% Percentile; Q3=75% Percentile; and SD=Standard Deviation.

^a=Number of subjects with non-missing data, used as the denominator.

The variable 'Has the subject ever experienced any diseases and/or surgeries?' will only use the data at screening.

Table 1.X. Demographic and Clinical Characteristics Summary

Baseline Demographics and Clinical Characteristics – Cohort 2 (540 mL)

Full Analysis Population – F1 (N=XXX)

FDP-1

Phase I

Special Note: Cohorts 1 and 2 are not masked; therefore, only one set of tables will be produced showing the unmasked treatment arm. For Cohort 3, there will be an Open and Closed session for the DSMB to protect the mask. For the Open session only, the Total Column will be shown with the table numbers having the word “(Open)” after the table number before the decimal. Open session tables will be produced by the blinded programmers. For the Closed session, the treatment arms will be masked as A and B. The table numbers will have the word “(Closed)” after the table number before the decimal. Closed session tables will be produced by the unblinded programmers. Final data analysis for Cohort 3, will use the labels FDP-ACDxFFP and FFPxFDP-ACD for the treatments after the study is unblinded and the word “(Closed)” will be removed from the table number.

Table 1.X (Open). Demographic and Clinical Characteristics Summary

Baseline Demographics and Clinical Characteristics – Cohort 3 (810 mL)

Full Analysis Population – F1 (N=XXX)

FDP-1

Phase I

Table 1.X (Closed). Demographic and Clinical Characteristics Summary

Baseline Demographics and Clinical Characteristics – Cohort 3 (810 mL)

Full Analysis Population – F1 (N=XXX)

FDP-1

Phase I

Note: Abbreviations: N=Number of subjects in the population; Q1=25% Percentile; Q3=75% Percentile; and SD=Standard Deviation.

^a=Number of subjects with non-missing data, used as the denominator.

The variable ‘Has the subject ever experienced any diseases and/or surgeries?’ will only use the data at screening.

Table 1.16. – Table 1.20 (Open). Demographic and Clinical Characteristics Summary - Overall Baseline Demographic and Clinical Characteristics – Overall Full Analysis Population – F1 (N=XXX)
FDP - 1
Phase I

		FDP-CPD		FDP-ACD		
Demographic and Clinical Characteristics Parameter		Cohort 1 270 mL (N = XX)	Cohort 2 540 mL (N = XX)	Cohort 1 270 mL (N = XX)	Cohort 2 540 mL (N = XX)	Cohort 3 810 mL (N = XX)
Sex n (%)	n ^a	XX	XX	XX	XX	XX
	F	XX(X.X)	XX(X.X)	XX(X.X)	XX(X.X)	XX(X.X)
	M	XX(X.X)	XX(X.X)	XX(X.X)	XX(X.X)	XX(X.X)
	Missing	XX	XX	XX	XX	XX
Age (years)	n ^a	XX	XX	XX	XX	XX
	Mean	XX.X	XX.X	XX.X	XX.X	XX.X
	SD	XX.X	XX.X	XX.X	XX.X	XX.X
	Median	XX.X	XX.X	XX.X	XX.X	XX.X
	Q1, Q3	XX,XX	XX,XX	XX,XX	XX,XX	XX,XX
	Min, Max	XX,XX	XX,XX	XX,XX	XX,XX	XX,XX
	Missing	XX	XX	XX	XX	XX
Race n (%)	n ^a	XX	XX	XX	XX	XX
	American Indian or Alaska Native	XX(X.X)	XX(X.X)	XX(X.X)	XX(X.X)	XX(X.X)
	Asian	XX(X.X)	XX(X.X)	XX(X.X)	XX(X.X)	XX(X.X)
	Black or African American	XX(X.X)	XX(X.X)	XX(X.X)	XX(X.X)	XX(X.X)
	Native Hawaiian or Other Pacific Islander	XX(X.X)	XX(X.X)	XX(X.X)	XX(X.X)	XX(X.X)
	White	XX(X.X)	XX(X.X)	XX(X.X)	XX(X.X)	XX(X.X)
	Multiple	XX(X.X)	XX(X.X)	XX(X.X)	XX(X.X)	XX(X.X)
	Missing	XX	XX	XX	XX	XX
Ethnicity n (%)	n ^a	XX	XX	XX	XX	XX
	Hispanic	XX(X.X)	XX(X.X)	XX(X.X)	XX(X.X)	XX(X.X)
	Non-Hispanic or Latino	XX(X.X)	XX(X.X)	XX(X.X)	XX(X.X)	XX(X.X)
	Missing	XX	XX	XX	XX	Xx
Is the subject of childbearing potential? n (%)	n ^a	XX	XX	XX	XX	Xx
	Yes	XX(X.X)	XX(X.X)	XX(X.X)	XX(X.X)	XX(X.X)
	No	XX(X.X)	XX(X.X)	XX(X.X)	XX(X.X)	XX(X.X)
	Missing	XX	XX	XX	XX	Xx
Blood Type n (%)	n ^a	XX	XX	XX	XX	Xx
	A	XX(X.X)	XX(X.X)	XX(X.X)	XX(X.X)	XX(X.X)
	B	XX(X.X)	XX(X.X)	XX(X.X)	XX(X.X)	XX(X.X)
	AB	XX(X.X)	XX(X.X)	XX(X.X)	XX(X.X)	XX(X.X)
	O	XX(X.X)	XX(X.X)	XX(X.X)	XX(X.X)	XX(X.X)
Rh Factor n (%)	n ^a	XX	XX	XX	XX	Xx

Note: Abbreviations: N= number of subjects in the population; Q1=25% Percentile; Q3= 75% Percentile; and SD=Standard Deviation.

^a=Number of subjects with non-missing data, used as the denominator.

The variable 'Has the subject ever experienced any diseases and/or surgeries?' will only use the data at screening.

		FDP-CPD		FDP-ACD		
Demographic and Clinical Characteristics	Parameter	Cohort 1 270 mL (N = XX)	Cohort 2 540 mL (N = XX)	Cohort 1 270 mL (N = XX)	Cohort 2 540 mL (N = XX)	Cohort 3 810 mL (N = XX)
	Negative	xx(x.x)	xx(x.x)	xx(x.x)	xx(x.x)	xx(x.x)
	Positive	xx(x.x)	xx(x.x)	xx(x.x)	xx(x.x)	xx(x.x)
Height (cm)	n ^a	xx	xx	xx	xx	Xx
	Mean	xx.X	xx.X	xx.X	xx.X	xx.X
	SD	xx.X	xx.X	xx.X	xx.X	xx.X
	Median	xx.X	xx.X	xx.X	xx.X	xx.X
	Q1, Q3	xx,xx	xx,xx	xx,xx	xx,xx	xx,xx
	Min, Max	xx,xx	xx,xx	xx,xx	xx,xx	xx,xx
	Missing	xx	xx	xx	xx	Xx
Weight (kg)	n ^a	xx	xx	xx	xx	Xx
	Mean	xx.X	xx.X	xx.X	xx.X	xx.X
	SD	xx.X	xx.X	xx.X	xx.X	xx.X
	Median	xx.X	xx.X	xx.X	xx.X	xx.X
	Q1, Q3	xx,xx	xx,xx	xx,xx	xx,xx	xx,xx
	Min, Max	xx,xx	xx,xx	xx,xx	xx,xx	xx,xx
	Missing	xx	xx	xx	xx	Xx
BMI n (%)	n ^a	xx	xx	xx	xx	Xx
	Underweight (<18.5)	xx(x.x)	xx(x.x)	xx(x.x)	xx(x.x)	xx(x.x)
	Normal (18.5-<25)	xx(x.x)	xx(x.x)	xx(x.x)	xx(x.x)	xx(x.x)
	Overweight (25.0-<30)	xx(x.x)	xx(x.x)	xx(x.x)	xx(x.x)	xx(x.x)
	Obese (≥ 30)	xx(x.x)	xx(x.x)	xx(x.x)	xx(x.x)	xx(x.x)
	Missing	xx	xx	xx	xx	Xx
BMI (kg/m²)	n ^a	xx	xx	xx	xx	Xx
	Mean	xx.X	xx.X	xx.X	xx.X	xx.X
	SD	xx.X	xx.X	xx.X	xx.X	xx.X
	Median	xx.X	xx.X	xx.X	xx.X	xx.X
	Q1, Q3	xx,xx	xx,xx	xx,xx	xx,xx	xx,xx
	Min, Max	xx,xx	xx,xx	xx,xx	xx,xx	xx,xx
	Missing	xx	xx	xx	xx	Xx
Has the subject ever experienced any diseases and/or surgeries?	n ^a	xx	xx	xx	xx	Xx
	Yes	xx(x.x)	xx(x.x)	xx(x.x)	xx(x.x)	xx(x.x)
	No	xx(x.x)	xx(x.x)	xx(x.x)	xx(x.x)	xx(x.x)

Note: Abbreviations: N= number of subjects in the population; Q1=25% Percentile; Q3= 75% Percentile; and SD=Standard Deviation.

^a=Number of subjects with non-missing data, used as the denominator.

The variable 'Has the subject ever experienced any diseases and/or surgeries?' will only use the data at screening.

Table 1.16. – Table 1.20 (Closed). Demographic and Clinical Characteristics Summary - Overall Baseline Demographic and Clinical Characteristics – Overall Full Analysis Population – F1 (N=XXX)

**FDP - 1
Phase I**

		FDP-CPD		FDP-ACD		Cohort 3	
Demographic and Clinical Characteristics Parameter		Cohort 1 270 mL (N = XX)	Cohort 2 540 mL (N = XX)	Cohort 1 270 mL (N = XX)	Cohort 2 540 mL (N = XX)	A 810 mL (N = XX)	B 810 mL (N = XX)
Sex n (%)	n ^a	xx	xx	xx	xx	xx	xx
	F	xx(x.x)	xx(x.x)	xx(x.x)	xx(x.x)	xx(x.x)	xx(x.x)
	M	xx(x.x)	xx(x.x)	xx(x.x)	xx(x.x)	xx(x.x)	xx(x.x)
	Missing	xx	xx	xx	xx	xx	xx
Age (years)	n ^a	xx	xx	xx	xx	xx	xx
	Mean	xx.x	xx.x	xx.x	xx.x	xx.x	xx.x
	SD	xx.x	xx.x	xx.x	xx.x	xx.x	xx.x
	Median	xx.x	xx.x	xx.x	xx.x	xx.x	xx.x
	Q1, Q3	xx,xx	xx,xx	xx,xx	xx,xx	xx,xx	xx,xx
	Min, Max	xx,xx	xx,xx	xx,xx	xx,xx	xx,xx	xx,xx
	Missing	xx	xx	xx	xx	xx	xx
Race n (%)	n ^a	xx	xx	xx	xx	xx	xx
	American Indian or Alaska Native	xx(x.x)	xx(x.x)	xx(x.x)	xx(x.x)	xx(x.x)	xx(x.x)
	Asian	xx(x.x)	xx(x.x)	xx(x.x)	xx(x.x)	xx(x.x)	xx(x.x)
	Black or African American	xx(x.x)	xx(x.x)	xx(x.x)	xx(x.x)	xx(x.x)	xx(x.x)
	Native Hawaiian or Other Pacific Islander	xx(x.x)	xx(x.x)	xx(x.x)	xx(x.x)	xx(x.x)	xx(x.x)
	White	xx(x.x)	xx(x.x)	xx(x.x)	xx(x.x)	xx(x.x)	xx(x.x)
	Multiple	xx(x.x)	xx(x.x)	xx(x.x)	xx(x.x)	xx(x.x)	xx(x.x)
	Missing	xx	xx	xx	xx	xx	xx
Ethnicity n (%)	n ^a	xx	xx	xx	xx	xx	xx
	Hispanic	xx(x.x)	xx(x.x)	xx(x.x)	xx(x.x)	xx(x.x)	xx(x.x)
	Non-Hispanic or Latino	xx(x.x)	xx(x.x)	xx(x.x)	xx(x.x)	xx(x.x)	xx(x.x)
	Missing	xx	xx	xx	xx	xx	xx
Is the subject of childbearing potential? n (%)	n ^a	xx	xx	xx	xx	xx	xx
	Yes	xx(x.x)	xx(x.x)	xx(x.x)	xx(x.x)	xx(x.x)	xx(x.x)
	No	xx(x.x)	xx(x.x)	xx(x.x)	xx(x.x)	xx(x.x)	xx(x.x)
	Missing	xx	xx	xx	xx	xx	xx
Blood Type n (%)	n ^a	xx	xx	xx	xx	xx	xx
	A	xx(x.x)	xx(x.x)	xx(x.x)	xx(x.x)	xx(x.x)	xx(x.x)
	B	xx(x.x)	xx(x.x)	xx(x.x)	xx(x.x)	xx(x.x)	xx(x.x)
	AB	xx(x.x)	xx(x.x)	xx(x.x)	xx(x.x)	xx(x.x)	xx(x.x)
	O	xx(x.x)	xx(x.x)	xx(x.x)	xx(x.x)	xx(x.x)	xx(x.x)
Rh Factor n (%)	n ^a	xx	xx	xx	xx	xx	xx
	Negative	xx(x.x)	xx(x.x)	xx(x.x)	xx(x.x)	xx(x.x)	xx(x.x)

Note: Abbreviations: N= number of subjects in the population; Q1=25% Percentile; Q3= 75% Percentile; and SD=Standard Deviation.

^a=Number of subjects with non-missing data, used as the denominator.

The variable 'Has the subject ever experienced any diseases and/or surgeries?' will only use the data at screening.

		FDP-CPD		FDP-ACD		Cohort 3	
Demographic and Clinical Characteristics Parameter		Cohort 1 270 mL (N = XX)	Cohort 2 540 mL (N = XX)	Cohort 1 270 mL (N = XX)	Cohort 2 540 mL (N = XX)	A 810 mL (N = XX)	B 810 mL (N = XX)
Height (cm)	Positive	xx(x.x)	xx(x.x)	xx(x.x)	xx(x.x)	xx(x.x)	xx(x.x)
	n ^a	xx	xx	xx	xx	xx	xx
	Mean	xx.x	xx.x	xx.x	xx.x	xx.x	xx.x
	SD	xx.x	xx.x	xx.x	xx.x	xx.x	xx.x
	Median	xx.x	xx.x	xx.x	xx.x	xx.x	xx.x
	Q1, Q3	xx,xx	xx,xx	xx,xx	xx,xx	xx,xx	xx,xx
	Min, Max	xx,xx	xx,xx	xx,xx	xx,xx	xx,xx	xx,xx
Weight (kg)	Missing	xx	xx	xx	xx	xx	xx
	n ^a	xx	xx	xx	xx	xx	xx
	Mean	xx.x	xx.x	xx.x	xx.x	xx.x	xx.x
	SD	xx.x	xx.x	xx.x	xx.x	xx.x	xx.x
	Median	xx.x	xx.x	xx.x	xx.x	xx.x	xx.x
	Q1, Q3	xx,xx	xx,xx	xx,xx	xx,xx	xx,xx	xx,xx
	Min, Max	xx,xx	xx,xx	xx,xx	xx,xx	xx,xx	xx,xx
BMI n (%)	Missing	xx	xx	xx	xx	xx	xx
	n ^a	xx	xx	xx	xx	xx	xx
	Underweight (<18.5)	xx(x.x)	xx(x.x)	xx(x.x)	xx(x.x)	xx(x.x)	xx(x.x)
	Normal (18.5-<25)	xx(x.x)	xx(x.x)	xx(x.x)	xx(x.x)	xx(x.x)	xx(x.x)
	Overweight (25.0-<30)	xx(x.x)	xx(x.x)	xx(x.x)	xx(x.x)	xx(x.x)	xx(x.x)
	Obese (≥30)	xx(x.x)	xx(x.x)	xx(x.x)	xx(x.x)	xx(x.x)	xx(x.x)
	Missing	xx	xx	xx	xx	xx	xx
BMI (kg/m²)	n ^a	xx	xx	xx	xx	xx	xx
	Mean	xx.x	xx.x	xx.x	xx.x	xx.x	xx.x
	SD	xx.x	xx.x	xx.x	xx.x	xx.x	xx.x
	Median	xx.x	xx.x	xx.x	xx.x	xx.x	xx.x
	Q1, Q3	xx,xx	xx,xx	xx,xx	xx,xx	xx,xx	xx,xx
	Min, Max	xx,xx	xx,xx	xx,xx	xx,xx	xx,xx	xx,xx
	Missing	xx	xx	xx	xx	xx	xx
Has the subject ever experienced any diseases and/or surgeries?	n ^a	xx	xx	xx	xx	xx	xx
	Yes	xx(x.x)	xx(x.x)	xx(x.x)	xx(x.x)	xx(x.x)	xx(x.x)
	No	xx(x.x)	xx(x.x)	xx(x.x)	xx(x.x)	xx(x.x)	xx(x.x)

Programming Note: The table will be repeated for all analysis populations that are determined to be on a different set of subjects as described in Section 4.2 (Table 1.17 – Table 1.20). Table numbers may differ depending on how many tables are produced and may not exactly match the SAP. The titles for the tables will be the same for the other populations with the name of the population changing based on the population being used. Final data analysis for Cohort 3, will use the labels FDP-ACDxFPP and FFPxFDP-ACD for the treatments after the study is unblinded and the word “(Closed)” will be removed from the table number.

Note: Abbreviations: N= number of subjects in the population; Q1=25% Percentile; Q3= 75% Percentile; and SD=Standard Deviation.

^a=Number of subjects with non-missing data, used as the denominator.

The variable ‘Has the subject ever experienced any diseases and/or surgeries?’ will only use the data at screening.

Table 1.21 (Open). Analysis Populations and Subject Disposition

	FDP-CPD (270 mL) n (%)	FDP-ACD (270 mL) n (%)	FDP-CPD (540 mL) n (%)	FDP-ACD (540 mL) n (%)	Cohort 3 (810 mL) n (%)	Overall n (%)
Analysis Populations						
Full Analysis Population – F1 [a]	xx (xx.x)	xx (xx.x)				
Full Analysis Population – F2 [b]	xx (xx.x)	xx (xx.x)				
Safety Population – S1 [c]	xx (xx.x)	xx (xx.x)				
Safety Population – S2 [d]	xx (xx.x)	xx (xx.x)				
Safety Population – S3 [e]	xx (xx.x)	xx (xx.x)				
Completed the Study [f]	xx (xx.x)	xx (xx.x)				
Did Not Complete the Study [f]	xx (xx.x)	xx (xx.x)				
Primary Reason for Discontinuation [g]						
Adverse Event	xx (xx.x)	xx (xx.x)				
Death	xx (xx.x)	xx (xx.x)				
Lost to Follow-up	xx (xx.x)	xx (xx.x)				
...	xx (xx.x)	xx (xx.x)				
...	xx (xx.x)	xx (xx.x)				
...	xx (xx.x)	xx (xx.x)				

Note: Percents are based on the full analysis population – F1.

[a] The full analysis (F1) population includes all subjects that were enrolled, including subjects who were prematurely withdrawn from the study prior to the Infusion Visit and were never infused (F1).

[b] Enrolled and presented for treatment at the Infusion Visit (F2).

[c] The safety population (S1) includes all subjects who received any volume of infused product (in Cohort 3, this includes those who received a partial dose at either infusion visit).

[d] The safety population (S2) includes all subjects who received full infusion and have at least one outcome measure.

[e] The safety population (S3) includes all subjects who receive the full infusion dose and can be fully evaluated, because in Cohorts 1 and 2 the subjects minimally completed the 7-day follow-up visit and in Cohort 3 the subjects had both complete infusion doses and minimally completed the 7-day follow-up visit after the second infusion. (Per protocol population.)

[f] Denominator is the number of subjects that were infused based on the S1 population.

[g] Denominator is the number of subjects that did not complete the study.

Table 1.21 (Closed). Analysis Populations and Subject Disposition

	FDP-CPD (270 mL) n (%)	FDP-ACD (270 mL) n (%)	FDP-CPD (540 mL) n (%)	FDP-ACD (540 mL) n (%)	A (810 mL) n (%)	B (810 mL) n (%)	Overall n (%)
Analysis Populations							
Full Analysis Population – F1 [a]	xx (xx.x)	xx (xx.x)	xx (xx.x)	xx (xx.x)	xx (xx.x)	xx (xx.x)	xx (xx.x)
Full Analysis Population – F2 [b]	xx (xx.x)	xx (xx.x)	xx (xx.x)	xx (xx.x)	xx (xx.x)	xx (xx.x)	xx (xx.x)
Safety Population – S1 [c]	xx (xx.x)	xx (xx.x)	xx (xx.x)	xx (xx.x)	xx (xx.x)	xx (xx.x)	xx (xx.x)
Safety Population – S2 [d]	xx (xx.x)	xx (xx.x)	xx (xx.x)	xx (xx.x)	xx (xx.x)	xx (xx.x)	xx (xx.x)
Safety Population – S3 [e]	xx (xx.x)	xx (xx.x)	xx (xx.x)	xx (xx.x)	xx (xx.x)	xx (xx.x)	xx (xx.x)
Completed the Study [f]	xx (xx.x)	xx (xx.x)	xx (xx.x)	xx (xx.x)	xx (xx.x)	xx (xx.x)	xx (xx.x)
Did Not Complete the Study [f]	xx (xx.x)	xx (xx.x)	xx (xx.x)	xx (xx.x)	xx (xx.x)	xx (xx.x)	xx (xx.x)
Primary Reason for Discontinuation [g]							
Adverse Event	xx (xx.x)	xx (xx.x)	xx (xx.x)	xx (xx.x)	xx (xx.x)	xx (xx.x)	xx (xx.x)
Death	xx (xx.x)	xx (xx.x)	xx (xx.x)	xx (xx.x)	xx (xx.x)	xx (xx.x)	xx (xx.x)
Lost to Follow-up	xx (xx.x)	xx (xx.x)	xx (xx.x)	xx (xx.x)	xx (xx.x)	xx (xx.x)	xx (xx.x)
...	xx (xx.x)	xx (xx.x)	xx (xx.x)	xx (xx.x)	xx (xx.x)	xx (xx.x)	xx (xx.x)
...	xx (xx.x)	xx (xx.x)	xx (xx.x)	xx (xx.x)	xx (xx.x)	xx (xx.x)	xx (xx.x)
...	xx (xx.x)	xx (xx.x)	xx (xx.x)	xx (xx.x)	xx (xx.x)	xx (xx.x)	xx (xx.x)

